3.1 Primary Objective

The primary objective of this study is to determine whether the PSIS or deep humeral harvest produces a greater cellular harvest in patients undergoing rotator cuff repair.

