3.2 Secondary Objective

The secondary objective is to determine if prone verses lateral decubitus participant positioning influences the quantity of harvested cells from the PSIS.

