3.3 Primary Effectiveness Endpoints

The primary effectiveness endpoints of this study include cellular content measures of cBMA collected from each extraction site (as outlined in section 6.2).

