3.4 Secondary Effectiveness Endpoints

The secondary effectiveness endpoints of this study include cellular content measures of cBMA collected from each anatomical position (as outlined in section 6.2).

4 Hypotheses

4.1 Null Hypothesis:

H_0 - Participants will have similar cellular content (*in vitro*) in bone marrow aspirate taken from the PSIS and from deep humeral harvest. Additionally, patient positioning will not affect the cellular content of bone marrow from the PSIS.

4.2 Alternative Hypothesis:

H_1 - Participants will not have similar cellular content (*in vitro*) in bone marrow aspirate taken from the PSIS and from deep humeral harvest. Additionally, patient positioning will affect the cellular content of bone marrow from the PSIS.

5 Participant Recruitment and Screening

5.1 Screening Process:

Once interested participants are identified and prescreened, a screening visit will be scheduled (visit 1). During the screening visit, a screening form will be completed which includes the inclusion and exclusion criterion below. If an individual answers "yes" to any of the initial screening exclusion questions, they will be informed that they do not qualify for the study, and they will be informed that they can keep their screening form and their medical care will not be adversely affected by not enrolling in the study. If all answers are "no" then the form will be placed in the study documents and the enrollment process will continue.

5.1.1 Inclusion Criteria:

- 18-80 years of age
- Diagnosis of a rotator cuff tear requiring arthroscopic rotator cuff repair

5.1.2 Exclusion Criteria:

- Patients who require superior capsular reconstruction or revision rotator cuff repair
- Diabetes
- Immune disorders

- Past medical history of a metastatic or other cancer which required chemotherapy/radiation therapy
- Rheumatoid arthritis
- Is unable to comprehend the study documents or give informed consent

Once the screening requirements are met, the informed consent form will be provided to the participant on paper or electronically via REDCap for review ensure the volunteer understands the details of the study including the benefits and risk factors. The subject will be provided sufficient time to consent and sign the informed consent form (ICF). The principal investigator (PI) and study/research team will be available to answer any questions or provide clarifications during the informed consent process.

5.2 Informed Consent 21 CFR 50

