viewing from the standard posterior portal in the subacromial space, a spinal needle will be used to localize the location and trajectory for placement of the first suture anchor for the rotator cuff repair. Once the placement of the proposed anterior suture anchor is confirmed, the 11-gauge bone marrow harvest needle will be placed into this location and the arm adducted. The needle will then be advanced into the humeral diaphysis as far as the needle length allows. Two 30 mL syringes will be pre-filled with 4 mL of ACD-A and used to harvest 60 mL of bone marrow aspirate. The bone marrow samples will then be processed independently using the Arthrex Angel blood processing system (Arthrex, Naples, FL) using the 12% hematocrit setting with two separate disposables. One mL of cBMA from each harvest site will be removed and sent to the AREF RMC for analysis. The remaining cBMA will be used to augment the rotator cuff repair surgery.

6.2 Cellular Analysis:

Cellular analysis of each cBMA sample from the two collection sites per participant will include a Complete Blood Cell (CBC) count, a Total Nucleated Cell (TNC), viability count, and cell culture analysis.

The CBC count will be performed using an automated hemocytometer (XN-350; Sysmex, Kungsbacka, Sweden) and will include red blood cell (RBC), white blood cell (WBC), monocyte, platelet, and hematopoietic progenitor cell (HPC) concentration.

The TNC and viability count will be performed using an automated cell counter.

Cell culture experiments will include Colony Forming Unit-fibroblast (CFU-F) counts and the potential for additional stem or progenitor cell analysis procedures. If stem or progenitor cells are observed during culturing, additional experiments will be conducted to analyze differentiation potential (differentiation assays) and cell-surface markers (flow cytometry).

7 Review of Safety

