Descriptive statistics will be compiled for all numeral measures (Demographics, CBC, TNC, viability, CFU-F). Data will be analyzed for differences between experimental groups (PSIS v. deep humeral harvest, Prone vs. lateral decubitus positions) using 1-Way ANOVA and appropriate post-hoc analysis procedures (ex: Tukey's Honestly Significant Difference (HSD)). A significant p-value of < 0.05 for rejecting the null hypothesis will be used for all measures.

11 Quality Control and Assurance

All protocols will be monitored and analyzed data will be checked for accuracy by the principal investigator and /or a designated AREF research team member. All medical data will be kept in compliance with HIPAA guidelines.

12 References

1. Akpancar, S., et al., *The Current Perspectives of Stem Cell Therapy in Orthopedic Surgery*. Arch Trauma Res, 2016. **5**(4): p. e37976.
2. Marycz, K., et al., *Endurance Exercise Mobilizes Developmentally Early Stem Cells into Peripheral Blood and Increases Their Number in Bone Marrow: Implications for Tissue Regeneration*. Stem Cells Int, 2016. **2016**: p. 5756901.
3. Rochefort, G.Y., et al., *Multipotential mesenchymal stem cells are mobilized into peripheral blood by hypoxia*. Stem Cells, 2006. **24**(10): p. 2202-8.
4. Hauser, R.A. and A. Orloffsky, *Regenerative injection therapy with whole bone marrow aspirate for degenerative joint disease: a case series*. Clin Med Insights Arthritis Musculoskelet Disord, 2013. **6**: p. 65-72.
5. Hernigou, P., et al., *Biologic augmentation of rotator cuff repair with mesenchymal stem cells during arthroscopy improves healing and prevents further tears: a case-controlled study*. Int Orthop, 2014. **38**(9): p. 1811-8.
6. Hernigou, P., et al., *Cell therapy of hip osteonecrosis with autologous bone marrow grafting*. Indian Journal of Orthopaedics, 2008. **43**(1): p. 40-45.
7. Hernigou, P., et al., *Percutaneous autologous bone-marrow grafting for nonunions*. Journal of Bone and Joint Surgery, 2005. **87**(7): p. 1430-1437.
8. Saw, K.Y., et al., *Articular cartilage regeneration with autologous peripheral blood stem cells versus hyaluronic acid: a randomized controlled trial*. Arthroscopy, 2013. **29**(4): p. 684-94.
9. Vangsness, C.T., Jr., H. Sternberg, and L. Harris, *Umbilical Cord Tissue Offers the Greatest Number of Harvestable Mesenchymal Stem Cells for Research and Clinical Application: A Literature Review of Different Harvest Sites*. Arthroscopy, 2015. **31**(9): p. 1836-43.

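### Eight cell measures are all primary and each is tested at 0.05, with none named to decide which site gives the greater harvest

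*Protocol*

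**What the plan says.** The primary objective (protocol section 3.1) is a single directional question: to "determine whether the PSIS or deep humeral harvest produces a greater cellular harvest in patients undergoing rotator cuff repair". The primary endpoints are a set, not one measure. Section 3.3 reads "The primary effectiveness endpoints of this study include cellular content measures of cBMA collected from each extraction site" and points to section 6.2 for the list.

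Section 6.2 names eight quantities. The blood count "will include red blood cell (RBC), white blood cell (WBC), monocyte, platelet, and hematopoietic progenitor cell (HPC) concentration", which is five. Total nucleated cells (TNC), viability and CFU-F make eight. The section also mentions "the potential for additional stem or progenitor cell analysis procedures", and differentiation and cell-surface marker work if stem or progenitor cells are seen in culture.

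Section 3.4 uses the same set for the secondary question of patient position. Section 10 then fixes the decision rule: "A significant p-value of < 0.05 for rejecting the null hypothesis will be used for all measures". It plans one-way ANOVA with a post-hoc procedure, for which Tukey's HSD is the example. Its list of measures for descriptive statistics, apart from demographics, contains only the blood count, TNC, viability and CFU-F.

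**The concern.** Harvest in section 3.1 could mean any of the eight quantities, and they are not interchangeable. Viability does not count harvested cells. Red cell and platelet concentrations rank formally equal to CFU-F, although the introduction justifies the study by progenitor-cell yield. Suppose some measures differ between sites at 0.05 and others do not. The protocol then gives no rule for which of them answers the primary objective, and a report could lead with whichever measure reached significance.

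Tukey's HSD does not help. It protects comparisons among groups for one measure and does nothing across measures. What is at stake is whether a statement that one site is better rests on a test chosen in advance. The same holds for the statement on position.

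**Working it through.** **Inputs from the protocol.** Significance level 0.05 for each measure (section 10). Named measures: 5 (blood count) + 1 (TNC) + 1 (viability) + 1 (CFU-F) = 8 (section 6.2). Thirty patients, each sampled at both sites, 15 with prone and 15 with lateral PSIS harvest (section 2). The protocol states no family-wise level, power, effect size or correlation, so there is no figure of its own to reproduce beyond the 0.05. All correlations below are assumptions.

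**Step 1: eight valid, independent 5% tests.** Chance of at least one false positive = 1 - (1 - 0.05)^8 = 1 - 0.95^8 = 1 - 0.663 = 0.337.

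**Step 2: correlated measures.** Eight two-sided z-tests with a common correlation, 1,000,000 draws:

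| Between-measure correlation | 0 | 0.3 | 0.5 | 0.7 | 0.9 |
|---|---|---|---|---|---|
| At least one p < 0.05 | 33.7% | 30.0% | 25.0% | 19.1% | 12.0% |

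**Step 3: the trial's own layout.** Simulation with no true differences: 30 patients with both sites, eight normal measures, 40,000 trials per setting, between-measure correlation from 0 to 0.9.

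- Position, 15 v 15: 33.9% down to 11.8%.
- Site, paired t-test: 33.8% down to 12.2%.
- Site, unpaired ANOVA as section 10 is worded:

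| Within-patient correlation between sites | Between-measure 0 | 0.3 | 0.5 | 0.7 | 0.9 |
|---|---|---|---|---|---|
| 0 | 33.4% | 30.2% | 25.1% | 19.4% | 12.1% |
| 0.3 | 15.2% | 13.8% | 11.8% | 9.0% | 5.4% |
| 0.5 | 5.3% | 5.0% | 4.3% | 3.6% | 2.0% |
| 0.7 | 0.6% or less | | | | |

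The unpaired figures fall because that test takes the variance of the mean difference as 2σ²/30. With both samples from the same patient it is 2σ²(1 - r)/30, where r is the within-patient correlation. Each single test then has a true error rate below 5%.

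**Step 4: another reading of section 10.** If it means one three-group ANOVA per measure (PSIS prone, PSIS lateral, humerus), the same simulation gives about 5% to 34% over the eight tests.

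**Step 5: the lists of measures.** Section 3.3 refers to section 6.2, which allows further assays. The descriptive list in section 10 has none of them. The closing rule in section 10 speaks of all measures without saying which list it means.

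**The case against.** **The analysis plan could settle this.** It could add detail, and none is at hand. But the protocol has itself fixed the primary set and the unadjusted threshold. A plan that picked one measure would be changing what section 3.3 says.

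**The primary test may not be inflated.** This stands. A reader might infer that the site conclusion carries a one-in-three risk of a false positive. The documents do not support that: the unpaired analysis as written can be conservative, and 33.7% needs independent measures and valid 5% tests. Position has no such offset.

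**The list may be closed.** A reader might infer that primary measures can be added without limit. The list in section 10 allows a closed reading, and the further work in section 6.2 is only possible or conditional. What stands is that the two sections differ.

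**The measures may agree.** A reader might expect contradictory verdicts. The protocol gives no ground to predict them. In the comparison cited in its introduction (PSIS against proximal humerus, a different site), both reported measures favoured PSIS, by 3.0 and 8.3 times. In a simulation with equal true effects of 0.2 to 0.5 SD of the paired differences on all eight measures, significant results in opposite directions occurred in under 1% of trials. The difficulty is choosing among measures, not a forecast conflict.

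**The hypotheses in section 4.** Section 4.1 adds position to the site null: "Additionally, patient positioning will not affect the cellular content of bone marrow from the PSIS". Read as a strict conjunction, a site effect without a position effect would fit neither H_0 nor H_1. But sections 3.1 to 3.4 and section 10 keep the two questions apart, so this is a drafting matter and not a failure of the design.

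**Conclusion.** The point holds and should be corrected. Eight named measures are all primary, each is tested at 0.05 without adjustment across measures, and none is designated to answer section 3.1. That follows from the text and needs no assumption about error rates.

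The size of the inflation does rest on assumptions. For position it is about 12% to 34%, for between-measure correlations from 0.9 down to 0. The same range applies to site if the pairing is kept. For site analysed as written, it runs from that range at within-patient correlation 0 to about 5% or less at 0.5 and above, so inflation there is possible but not shown. Even where the rate is low, the measure that carries the primary conclusion can still be selected after the results are known.

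**What to change.** Before any data are analysed:

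1. In section 3.3, name and justify one primary measure for the site comparison, tested at two-sided 0.05. The choice is the sponsor's; CFU-F, HPC or TNC are examples.
2. In section 3.4, name one lead measure for position.
3. In section 10, label every other measure, including any assay added under section 6.2, as exploratory, reported with estimates and 95% confidence intervals and no claim of significance. Align the lists in sections 6.2 and 10.
4. As a minor wording change, state the site and position hypotheses separately in section 4.

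The cost is wording only, with no new data or patients. The downside is that no formal significance claim can be made on the other measures. The lead measure loses no power.

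Keeping all eight primary with a Bonferroni level of 0.05/8 = 0.00625 would cost more. With 30 pairs, a paired test and 80% power, the detectable difference would rise from 0.53 to 0.70 SD of the paired differences.
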